Clinical study visits will occur at enrollment, a follow-up study visit at month-3, and an exit visit at 6-months post-enrollment. For participants who are prescribed buprenorphine, additional brief refill visits will occur at monthly intervals. All assessments will occur during in-person visits in the pilot clinic. Each study visit will consist of a short survey, an eligibility assessment for oral PrEP and MOUD, standard clinical care, and biological sample collections (i.e., DBS sample collection for research only, self-collected vaginal swabs for point-of-care STI testing, and blood samples for blood born infection testing). To test the impact of this pilot clinic model on improving uptake and sustained use of HIV prevention services, we will utilize medical record data and DBS drug (buprenorphine and tenofovir) levels. Prior to enrollment, participants will be asked to provide consent for participation in the study, review of electronic medical record (EMR) data, and review of pharmacy records. Consent will be collected using electronic data capture (REDCap) and participant data will be collected by medical record number (MRN) utilizing an EMR querying technology (Leaf) generated by the University of Washington as well as manual chart review. Participants meeting CDC eligibility criteria for PrEP will be counselled on HIV risk, offered HIV testing, and if negative and interested, oral PrEP will be prescribed per clinical guidelines. Additionally, participants with active self-reported use of opioids will be counselled on options for opioid use disorder treatment, and those interested in MOUD, will be provided with a prescription for buprenorphine-naloxone or buprenorphine, per clinical guidelines. Uptake of PrEP and buprenorphine will be measured by review of pharmacy and EMR records and will be defined by filling a prescription for PrEP or buprenorphine. In collaboration with [name] and the University of California San Francisco (UCSF) Hair Analytical Laboratory (HAL), we will measure sustained use of PrEP and buprenorphine via tenofovir disoproxil fumarate (TDF) and buprenorphine levels in samples of 150 hairs. The UCSF-HAL can simultaneously test for buprenorphine, fentanyl, and tenofovir from the same specimen, and we will measure these drug levels at 3- and 6- months to evaluate adherence to PrEP and buprenorphine. Additionally, dried blood spots (DBS) will be collected and archived to ensure that drug levels are collected during this study in the event there are any complications with hair testing.

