During or immediately following the visit, the clinic staff will fill out a visit summary report in REDCap, indicating the results of POC STI and HIV testing, any STI treatment given, if the participant was prescribed PrEP or reasons they were not prescribed PrEP, and if the participant was prescribed buprenorphine or reason the participant was not prescribed buprenorphine.

Follow-up study visits, Month 3 and Month 6 (Exit visit)

All patients will be asked to return to the clinic 3 months and 6 months following enrollment. At these follow-up study visits, patients will undergo additional counseling for HIV risk reduction

and treatment of opioid use disorder, as indicated based on their individual risk and substance use behaviors. At both the Month 3 and Month 6 visits, all patients will fill out a brief questionnaire self-reporting substance use and sexual behavior in the past three months. Participants who were previously prescribed PrEP through the venue-based clinic will fill out questions about their adherence to PrEP and barriers/facilitators to taking PrEP. Participants who were previously prescribed buprenorphine will similarly fill out questions about their adherence to buprenorphine and barriers/facilitators to taking buprenorphine. All participants who received a prescription for PrEP or buprenorphine will be asked to provide a 150-strand hair sample and a DBS sample for tenofovir and/or buprenorphine drug level checking. Any participant not previously initiated on PrEP or buprenorphine will be offered PrEP and/or buprenorphine at the follow-up study visits, as indicated per practice guidelines. Participants will be tested for STIs using POC testing, and any participant diagnosed with an STI will receive prompt treatment prior to leaving clinic, as outlined in the “Study Design: General Overview” section of this protocol. Additionally, participant will be offered laboratory-based STI testing of the oral and rectal sites. Participants who initiated PrEP will have phlebotomy performed for a 4th generation HIV antigen/antibody assay. Participants who did not initiate PrEP at baseline but initiate PrEP at month 3 or 6 will also have phlebotomy for serum creatinine and hepatitis B virus (HBV) serologies. Clinic staff will similarly address any immediate medical concerns of the participant, as per standard of care. At the end of each follow-up study visit, participants will be given a \$25 Visa gift card for their participation.

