	POC Trichomonas screening (self-collected vaginal swab)	X	X	X	
	POC CT/NG testing (self-collected vaginal swab)	X	X	X	
	Hair sample collection (for TFV and Bupe levels)	X	X	X	
	Dried Blood Spot (for TFV and Bupe levels)	X	X	X	
	Financial Incentive for Returning for Results (following study visits)	X ^b	X ^b	X ^b	X ^b
^a only for those who consent to billing/insurance claim					
^b If clinically indicated					

Lab Processing and Results Delivery

Study specific labs will include hair sample and DBS collection for detection of tenofovir and buprenorphine levels, as well as self-collected vaginal swabs for POC STI testing and POC fingerstick HIV and syphilis testing.

Hair testing:

Hair samples will be sent to the Hair Analytical Laboratory (HAL) at the University of California San Francisco (UCSF-HAL). The HAL uses liquid chromatography-tandem mass spectrometry (LC-MS/MS) for testing. The HAL has found high rates of acceptability and feasibility (>95%) of collecting hair samples among U.S. adolescents and women. Our group has experience with hair collection across studies and has found it acceptable.

HAL will test hair sample for tenofovir and buprenorphine levels, as indicated based on medications prescribed to each participant. Results of hair sample testing will be used for research purposes only to determine adherence to prescribed medications, and results will not be returned to the individual participant.

DBS testing:

Dried blood spots will be obtained at baseline and at quarterly follow-up visits (Month 3 and Month 6) using a lancet finger stick to express drops of blood onto a 5-spot DBS card. This will be done following collection of a blood droplets from finger for the HIV/syphilis rapid test. The card will be labeled with participant ID and transported to PI's locked office where they will be securely stored for possible TFV and buprenorphine testing.

POC STI testing:

Chlamydia and Gonorrhea testing

Participants will give their self-collected vaginal swab specimen to clinic staff prior to survey completion. Participants will collect a vaginal swab in a private space in the study clinic. POC STI tests for *C. trachomatis* and *N. gonorrhoeae* will be available within 30 minutes using a small, FDA approved, CLIA waived PCR machine supplied by Binx Health. POC STI samples

will be processed in real time, with results delivered to participants during the study visit, and no samples stored.

Trichomoniasis testing

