Research Material Obtained from Participants

Individuals who are eligible and enroll in venue-based care will complete a baseline, 3-month and 6-month study visit. Data to be collected at those visits include information on demographics, risk factors for HIV, PrEP eligibility, prior use of PrEP, history of substance use, prior use of medications for opioid use disorder (MOUD), current use of MOUD, and self-reported adherence to PrEP and/or MOUD, as indicated. Participants will also provide information on their experience accessing venue-based care, including acceptability and perceived stigma associated with accessing venue-based care. POC HIV testing, POC STI testing, and standard of care labs for PrEP will be obtained at baseline, 3-months and 6-months. Hair samples and DBS samples to test for tenofovir and buprenorphine will be obtained at 3-month and 6-month visits. A review of the participants medical and pharmacy records will be conducted.

Assessment data will be collected directly onto iPads used by research team members. We will utilize the Research Electronic Data Capture (REDCap) system through the University of Washington's Institute of Translational Health Services (ITHS) to log and store data.

Women who are started on buprenorphine therapy will also return for monthly refill visits, during which time no additional study data will be collected.

Risks to Human Subjects

There are limited physical risks to study subjects beyond what is incurred during standard primary care. Participants may experience mild bruising or pain at the site of point of care finger prick testing (e.g., POC HIV and syphilis testing, DBS sampling), or at the site of phlebotomy draws. Participants who choose to initiate on oral PrEP and/or buprenorphine will be at risk of experiencing established side effects, as outlined in each drugs' prescribing materials.

Participants may experience psychological distress associated with discussing confidential topics such as sexual and drug use practices. Research medical team staff will be trained in trauma-informed care and to address psychological distress with a calm, non-judgmental attitude. We will take steps to minimize any psychological discomfort by ensuring confidentiality as described below. We will only enroll patients who understand the study procedures and are willing to participate.

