 - b. Participants who accept prescriptions for MOUD at multiple points throughout the study will only be counted once when calculating uptake.
 - c. Final analysis will present uptake as a percentage (proportion).
3. Evaluate sustained use of PrEP
 - a. PrEP: Dried blood spot (DBS) samples were obtained at each visit to assess PrEP adherence via tenofovir-diphosphate (TFV-DP) concentrations. Sustained use was defined as >4 doses/week, resulting in a DBS TFV-DP concentration of >700 fmol/sample at 3 and/or 6 months post-enrollment among those prescribed PrEP at a preceding study visit.
 - b. Final analysis will present sustained use for both PrEP as a percentage (proportion).
4. Evaluate sustained use of MOUD
 - a. MOUD: DBS samples were obtained at each visit to assess MOUD adherence via buprenorphine and norbuprenorphine concentrations, both measured in ng/mL. Sustained use was defined as any buprenorphine and/or norbuprenorphine detected, resulting in a DBS >0 ng/mL concentration of buprenorphine and/or norbuprenorphine at 3 and/or 6 months post-enrollment among those prescribed MOUD at a preceding study visit.
 - b. Final analysis will present sustained use for MOUD as a percentage (proportion).
5. Evaluate STI treatment completion rate and time to completion after POC STI testing
 - a. Treatment completion will be defined as documented treatment following a reactive POC STI test (chlamydia, gonorrhea, syphilis, and/or trichomonas). Treatment will either be indicated in the Visit Clinical Summary from the study visit or noted during medical record chart review by a study provider. If treatment

was not provided on the same day as the visit, the date of treatment will be documented in the study database.

- b. Final analysis will present the treatment completion rate as the proportion of STIs where treatment was documented, by all STIs and by type.
 - c. Final analysis will present the time to treatment completion as the proportion of STIs treated same-day. Of the STIs not treated same-day, time to treatment will be presented as median number of days with an interquartile range.
6. Assess acceptability of pilot community-based care model
- a. Participants completed an acceptability survey following each study visit. Acceptability will be presented by study visit (i.e., enrollment, Month 3, and Month 6) as a proportion of all enrolled participants (N=50) who responded to the following questions:

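### Sustained use of PrEP and buprenorphine is assigned to hair in one part of the protocol and to dried blood spots in another, and only the dried-blood-spot version has a classification rule

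*Protocol*

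**What the plan says.** **Text that makes hair the measure.** The Protocol's Data Collection Overview says "we will measure sustained use of PrEP and buprenorphine via tenofovir disoproxil fumarate (TDF) and buprenorphine levels in samples of 150 hairs", with levels taken at months 3 and 6. DBS is collected and archived for use "in the event there are any complications with hair testing". Under Lab Processing and Results Delivery, the Hair testing paragraph has hair results determine adherence, and the DBS testing paragraph says of the cards that "they will be securely stored for possible TFV and buprenorphine testing".

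**Text that makes DBS the measure.** Study Design, General Overview, describes adherence monitoring by DBS and does not mention hair. An earlier sentence of the Data Collection Overview says that, to test the impact of the clinic, "we will utilize medical record data and DBS drug (buprenorphine and tenofovir) levels". Analysis Plan item 3a states: "Dried blood spot (DBS) samples were obtained at each visit to assess PrEP adherence via tenofovir-diphosphate (TFV-DP) concentrations". It sets the PrEP threshold at more than 700 fmol/sample at month 3 and/or 6. Item 4a does the same for MOUD, with any buprenorphine and/or norbuprenorphine above 0 ng/mL. Both denominators are participants prescribed the drug at a preceding study visit. Hair appears in neither item.

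**Sampling schedule and population.** Table 1 marks hair and DBS at months 0, 3 and 6, without the footnote for clinical indication that it uses on other rows. The DBS testing paragraph and item 3a also include baseline for DBS. Research Material Obtained from Participants gives a narrower schedule: "Hair samples and DBS samples to test for tenofovir and buprenorphine will be obtained at 3-month and 6-month visits". The section on the month 3 and month 6 visits limits who is sampled: "All participants who received a prescription for PrEP or buprenorphine will be asked to provide a 150-strand hair sample and a DBS sample".

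**The concern.** A primary outcome should have one specimen, one analyte and one rule for calling a participant a sustained user. Here the specimen depends on which section is read, and the analyte changes with it: tenofovir and buprenorphine in hair, tenofovir-diphosphate and buprenorphine and/or norbuprenorphine in DBS. A laboratory working from the methods would assay hair and hold the cards. An analyst working from the Analysis Plan would look for DBS concentrations that nobody was instructed to produce routinely. With two specimens per woman and no stated precedence, a reader of the eventual report also cannot tell whether the choice of specimen was planned.

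**Working it through.** The protocol states no figure on this point, so the check is mainly a comparison of text.

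| Section | Specimen for sustained use | Role of DBS | Cut-off |
|---|---|---|---|
| General Overview | DBS | Measure | None |
| Data Collection Overview, earlier sentence | DBS, with medical records | Measure | None |
| Data Collection Overview, later sentences | Hair | Archived reserve | None |
| Hair testing / DBS testing | Hair | Stored for possible testing | None |
| Analysis Plan items 3 and 4 | DBS | Sole definition | >700 fmol/sample (PrEP); >0 ng/mL (MOUD) |

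1. *Follow the hair text.* Hair is assayed, but no concentration in hair is tied to sustained use. The DBS thresholds do not carry over, because specimen and analyte differ. The outcome has no classification rule.
2. *Follow the Analysis Plan.* The rule is complete, but it needs DBS assays at months 3 and 6 that the laboratory text does not plan as routine.
3. *Look for a bridge.* The only link is the reserve clause. No section says that hair testing failed or was dropped, and none says what would count as a complication or who would decide.

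**Sampling conflicts.** Read literally, Table 1 gives 50 × 3 = 150 collections of each specimen. The narrow reading is prescribed women only, at months 3 and 6. Assume the prior clinic uptake in Background and rationale (33% PrEP, 49% buprenorphine), all prescribed at baseline, and no loss.

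- Full overlap of the two drugs: 0.49 × 50 = 24.5 women, × 2 visits = 49 collections.
- No overlap: (0.33 + 0.49) × 50 = 41 women, × 2 visits = 82 collections.

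The two schedules differ widely in workload. Neither changes the endpoint in items 3 and 4, which counts only women already prescribed and uses only months 3 and/or 6.

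**Illustration of sensitivity.** Assume the same uptake, all prescribed before month 6, and all retained.

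- PrEP: 0.33 × 50 = 16.5, about 17 women; 1/17 = 5.9 percentage points per woman.
- Buprenorphine: 0.49 × 50 = 24.5, about 25 women; 1/25 = 4.0 percentage points per woman.

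This shows what one changed classification does to a small denominator. It does not estimate disagreement between hair and DBS: the protocol gives no such rate, and without a hair cut-off disagreement cannot be defined.

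**The case against.** The best defence is that DBS is a foreseen contingency. The Data Collection Overview has "dried blood spots (DBS) will be collected and archived to ensure that drug levels are collected during this study in the event" of trouble with hair, so the cards exist and can be assayed, and the Analysis Plan may simply reflect that fallback in use. DBS is also named in the General Overview and in an earlier sentence of the Data Collection Overview, so hair may be the leftover text. This is a single-arm pilot reporting percentages, with no hypothesis test stated.

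Much of that stands, and it rules out several stronger readings.

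- *The DBS analysis could not be run.* Archived cards could still be assayed. What is missing is an instruction to do so.
- *The specimen was chosen after results were seen.* The Analysis Plan's past tense invites this inference, but items 6a and 7a use the same tense for surveys whose method is not in dispute. It may only mean that the section was drafted late. Since hair has no cut-off, it also offers no competing result without a new definition.
- *All 50 women are affected.* The denominators are women prescribed the drug at a preceding study visit. A woman first prescribed at month 6 counts toward uptake but cannot enter them.
- *The visit text contradicts baseline sampling.* The month 3 and month 6 section covers follow-up only and is silent on baseline. The schedule conflict comes from Research Material Obtained from Participants.

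The defence does not remove the conflict. The Analysis Plan presents DBS as the definition, not as a contingency, and nothing records that the contingency arose. A separate statistical analysis plan could add detail, but the protocol's own text would still contradict itself.

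**Conclusion.** The concern holds for the specimen. The protocol gives incompatible specimens for the two primary sustained-use outcomes, and only DBS has thresholds. The hair text yields no classification rule, and the Analysis Plan relies on assays not planned as routine. The effect on the result cannot be sized from the document. The figures of about 6 and 4 points per woman are conditional on uptake, timing of prescription and retention, and losses would make each woman count for more.

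The disagreements about who is sampled and whether baseline is included are real but secondary. A reader might infer that they bias the outcome; as items 3 and 4 define it, they do not. Nor does the document support a claim that the specimen was picked to suit the results. It leaves that question open, which is reason enough to ask for the date of the decision.

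**What to change.** 1. Name DBS as the single primary specimen for sustained use, since it alone has stated analytes and thresholds.
2. Reword the Data Collection Overview and the Hair testing and DBS testing paragraphs so that month 3 and month 6 cards from women prescribed PrEP or MOUD at a preceding study visit are assayed for the analytes in items 3 and 4.
3. Make hair a secondary measure with a cut-off stated in advance, or drop it.
4. State when DBS became the primary specimen and whether any assay result was known then.
5. Reconcile Table 1, the DBS testing paragraph, the visit descriptions, Research Material Obtained from Participants and item 3a on which visits and which participants are sampled.

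Assaying baseline cards to flag drug already present at entry is optional. It would add drug-level evidence to the baseline questionnaire, which asks about prior PrEP use and current MOUD use, but no defined endpoint needs it.

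The cost is wording plus routine DBS assays at months 3 and 6: on the illustrative uptake with all prescribed at baseline and no loss, about 49 to 82 cards. Dropping hair would offset some of this.

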Design: Pilot of novel care model for low-barrier care and adherence support for uptake and sustained use of biomedical HIV prevention and medications for opioid use disorder for women who inject drugs

Study Population: 50 female-identifying people ≥18 years of age and older who have ever injected drugs and are not known to be HIV-positive

Study Site: Community-based clinic on north Aurora Avenue in Seattle, WA

Primary Study Objectives:

1. Evaluate uptake of PrEP and MOUD
2. Evaluate sustained use of PrEP and MOUD
3. Evaluate treatment completion rate and time to completion after POC STI testing
4. Assess acceptability of pilot community-based care model
5. Assess acceptability of POC STI testing at community-based site.

Approach: We will conduct a pilot study of a community-based novel care model developed with community feedback and a community advisory board (CAB) co-design process during phase I of this project. We will enroll 50 female-identifying people and follow them for 6 months. We will assess uptake of PrEP and buprenorphine; POC STI testing and treatment completion rates; sustained use of PrEP and buprenorphine at months 3 and 6 (n=50). We will conduct surveys, guided by CFIR, to assess and characterize the acceptability and feasibility of venue-based primary and HIV prevention care among women who inject drugs (WWID).

Background and rationale

Women who inject drugs (WWID) experience frequent barriers to receiving primary care, especially sexual health and addiction services, because of perceived stigma, competing needs, and structural inequities within the healthcare system. Barriers to care among WWID are often exacerbated by the additional social chaos of unstable housing and engagement in transactional sex. These structural realities promote exclusion from traditional primary care systems, increase risk of HIV acquisition, and have led to rising rates of syphilis infections and overdose deaths among WWID in recent years. PrEP, buprenorphine, and STI control are key components of the End the HIV Epidemic prevention pillar and proven tools for reducing risk of HIV acquisition and opioid overdose, but uptake and sustained use of these interventions are low among WWID.

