POC STI test for *T. vaginalis* will be available within 10 minutes using individual FDA approved, CLIA waived lateral flow OSOM tests. This trichomonas rapid antigen test does not require equipment or a machine to process and is an immunochromatographic capillary-flow enzyme immunoassay based on trichomonas membrane proteins. Women will be instructed on self-collection of vaginal swab specimens. OSOM swabs will be placed into a sterile tube and processed on site. Results will be delivered in real-time and no samples will be stored.

Syphilis testing:

A rapid combination HIV/syphilis test (Chembio Diagnostic Systems) will be used to evaluate for *Treponema pallidum* antibodies. Any positive syphilis antibody test will be followed by laboratory-based confirmatory testing. Using shared decision making empiric treatment may be given (or initiating depending on stage of syphilis) prior to receiving confirmation of diagnosis.

HIV testing:

A rapid combination HIV/syphilis test (Chembio Diagnostic Systems) will be used to evaluate for incident HIV infections. Samples will be processed using the Chembio microreader kit. Any positive HIV test will be considered a possible seroconversion. Participants will be counseled on unconfirmed possible HIV diagnosis, the need to stop taking PrEP, and the need for laboratory-based confirmatory testing, which can be drawn on-site. All questions on HIV and HIV testing will be answered. Laboratory-based 4th generation HIV Ab/Ag test and HIV viral load will be drawn with samples sent to Harborview Medical Center, and participants will be linked to the SHE Clinic for next day follow-up.

Laboratory studies for clinical care:

Phlebotomy samples for standard of care labs will be centrifuged (as indicated), labeled, and transported back to Harborview Medical Center (HMC) on ice, where they will be delivered directly to the HMC lab for processing. Results will be reported out in the electronic medical record (EMR). The research team medical provider will call patients to deliver critical and urgent results. If the patient/participant is not reachable by phone, the research team medical provider will enlist the assistance of SHE Clinic staff to help in locating the patient/participant. Patients/participants will be asked to return the venue-based clinic the following week, or they can present to SHE Clinic during daytime hours, to follow-up on results.

Management of new diagnoses

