Participants found to have a diagnosis of chlamydia, gonorrhea, trichomoniasis, or syphilis will be offered prompt treatment. Treatment of gonorrhea will consist of intramuscular ceftriaxone 500mg x1 provided in clinic. Participants who test positive for chlamydia will be recommended to take doxycycline 100mg PO BID for 7 days; however, azithromycin 1g PO x1 will be offered as an alternative if participants are unable to complete a 7-day course of antibiotics. Similarly, participants who test positive for trichomonas will be recommended to take metronidazole 500mg PO BID for 7 days; however, metronidazole 2g PO x1 will be offered as an alternative if participants are unable to complete 7 days of antibiotics. Early syphilis will be treated with 2.4 million units of benzathine penicillin x1 or oral doxycycline 100mg BID for 14 days, pending benzathine penicillin availability. Late latent syphilis will be treated with 2.4 million units of benzathine penicillin weekly for 3 weeks or oral doxycycline 100mg BID for 28 days, pending benzathine penicillin availability. Single dose medications will be available in clinic. Otherwise

prescriptions will be sent to the Harborview Long-term Care Pharmacy for delivery to SHE Clinic within 48 hours. Participants with clinical concern for complicated STI (i.e., PID) will be offered prolonged treatment (single dose IM ceftriaxone and 2-week course of doxycycline and metronidazole) and referred for prompt follow up in SHE Clinic, another primary care clinic, or urgent care as indicated. Participants will be encouraged to tell partners to also be treated and made aware that these are reported by the lab to public health department. Should patients develop signs or symptoms of an STI at any point in the study they may come to the study clinic for additional laboratory-based testing (including for BV or candida infections) and treatment if needed.

Management of HIV

Patients who test positive for HIV on rapid or follow-up laboratory-based testing will be counseled on strategies to prevent transmission and referred to SHE Clinic for urgent evaluation and initiation of antiretroviral therapy, per clinical guidelines.

Management of pregnancy

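### Analysis Plan item 5 reports any documented STI treatment as completed treatment, so one of three penicillin injections for late latent syphilis scores as same-day completion

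*Protocol*

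**What the plan says.** **Objective.** Objective 3 in the protocol's list of primary objectives is "Evaluate treatment completion rate and time to completion after POC STI testing".

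**Outcome definition.** Analysis Plan item 5a treats completion as met when treatment is on record after a reactive point-of-care test for chlamydia, gonorrhea, syphilis or trichomonas. The record may be the visit's clinical summary or a later chart review, and a date is entered if treatment was not provided at the visit. Item 5b gives the proportion of infections with such a record, overall and by type. Item 5c gives time to completion as the proportion treated on the visit day, with median days and interquartile range for the rest.

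**Regimens.** Study Design: General Overview and Management of new diagnoses list the same regimens for the four infections. For late latent syphilis the choices are "benzathine penicillin weekly for 3 weeks or oral doxycycline 100mg BID for 28 days". For chlamydia, "Participants who test positive for chlamydia will be recommended to take doxycycline 100mg PO BID for 7 days"; likewise "participants who test positive for trichomonas will be recommended to take metronidazole 500mg PO BID for 7 days". Single-dose alternatives for these two are for women who cannot complete seven days.

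**Supply.** Management of new diagnoses keeps the single-dose drugs on hand at the visit. For every other regimen the same section sets a delivery route: "prescriptions will be sent to the Harborview Long-term Care Pharmacy for delivery to SHE Clinic within 48 hours".

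**Promise at follow-up.** Follow-up study visits, Month 3 and Month 6, states that "any participant diagnosed with an STI will receive prompt treatment prior to leaving clinic", referring back to the General Overview for how.

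**Syphilis before confirmation.** Under Syphilis testing, a positive rapid test goes to laboratory confirmation, and "empiric treatment may be given (or initiating depending on stage of syphilis) prior to receiving confirmation of diagnosis".

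**The concern.** The objective and item 5 both use the word completion, but the rule in item 5 is satisfied by the first documented treatment. For a single-dose regimen the two coincide. For a course with several dose dates they do not, and the Syphilis testing section itself separates treatment that is given from treatment that is only begun.

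The distinction matters here because the Background justifies point-of-care testing partly by its effect on incomplete or missing treatment, and says the existing clinic's impact has been limited by poor adherence and follow-through. A completion figure that cannot register missed second and third injections is blind to part of that problem. A reader of a published completion rate would take it to mean finished treatment.

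A smaller matter is that the follow-up section's statement on treatment before leaving does not fit the delivery route for multi-day oral courses.

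**Working it through.** The plan states no figure on this point, so there is nothing to reproduce. The check applies item 5 to the listed regimens.

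**1. Three weekly injections, first one at the visit.** Injection dates are day 0, 0 + 7 = day 7, and 7 + 7 = day 14.

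| Injections documented | Item 5a and 5c | By the regimen |
|---|---|---|
| 0 | not complete | not complete |
| 1 | complete, same day | not complete (1 of 3) |
| 2 | complete, same day | not complete (2 of 3) |
| 3 | complete, same day | complete, day 14 |

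The completion status is wrong in the second and third rows. The time to completion is also wrong in the fourth, where all injections were given. If the first injection is given later, on day d, item 5 records d and the course ends on day d + 14.

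**2. Effect on the reported figures.** Let N be the number of infections with a reactive test, T those with any documented treatment, S those treated on the visit day, L the three-injection courses started on the visit day, and M the three-injection courses with only one or two injections documented.

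- Item 5 rate: T/N. Rate if the three-injection course needs all three: (T − M)/N. Difference: M/N.
- Item 5 same-day share: S/N. Share without three-injection courses, none of which can finish that day: (S − L)/N. Difference: L/N.

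The protocol gives none of N, T, S, L or M, so no percentage follows. In the by-type results the effect falls entirely on syphilis.

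**3. Oral courses.** Four listed regimens are multi-day oral courses: doxycycline for 7, 14 and 28 days, and metronidazole for 7 days. Item 5a can date when such a course was provided. Nothing in it records whether the course was taken. Hence (T − M)/N is not a true completion rate either; it mixes finished injection courses with received oral courses.

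**4. Month 6 diagnoses.** Month 6 is the exit visit. Injections two and three would fall 7 and 14 days after it, or later if the first waits for confirmation. The protocol does not say how far beyond exit the chart review runs.

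**5. Promise and supply, side by side.** The follow-up section has every diagnosed infection treated before departure. Management of new diagnoses stocks single-dose drugs and delivers the rest to SHE Clinic within 48 hours. The first recommendations for chlamydia and trichomonas are 7-day courses, so a woman who follows them leaves without the drug. Item 5 already allows for this, since it records a later treatment date and reports median days.

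**The case against.** The strongest reply is that item 5 says openly what it counts. It defines its own term, the outcome is descriptive, and no test or threshold depends on it, so the choice between completion and receipt is partly one of vocabulary. This stands as a limit on severity. It does not remove the mismatch, because the objective and any headline result will carry the word completion.

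A reader might go further in three ways that the protocol does not support.

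- *That treatment before leaving is impossible for late latent syphilis.* The follow-up section promises that treatment is received, not finished, and refers to the General Overview, which lists the three-injection course. A first injection can satisfy it. Moreover, a reactive rapid test still awaits laboratory confirmation, so it may not yet be a diagnosis in the sense of that sentence.
- *That because five of the nine listed regimens outlast the visit day, most of the reported results are wrong.* That counts regimens, not cases, and no case mix is given. Four of the five are oral courses, whose later receipt item 5c already handles; for these only the label is loose. Misclassification that the chart could reveal is confined to the three-injection course.
- *That treatment will not be recorded at follow-up*, because the follow-up description of the visit summary omits the STI treatment mentioned at baseline. Table 1 has STI treatment and the provider clinical summary at months 0, 3 and 6, and item 5a names both the visit summary and chart review as sources. No data gap is shown.

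**Conclusion.** The point holds in a narrow form and is minor. Item 5 measures whether and when treatment was begun or received, and calls this completion. For the three-injection regimen the rule gives a wrong answer: one injection out of three is scored as complete on day 0, when the course ends on day 14 at the earliest. For oral courses the measure is receipt. For single-dose regimens there is no fault.

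This rests on reading item 5a as written, with no requirement to finish a course, and on the first injection being given at the visit, which the protocol permits but does not require. The effect is M/N on the rate and L/N on the same-day share, with both sizes unknown. Separately, the follow-up section and the supply arrangement conflict for delivered oral courses. That is a matter of wording and alters no reported number.

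**What to change.** **Objective 3 and item 5.** Report the existing measure as treatment initiation or receipt: the rate, the same-day share, and median days for the rest, using the date the drug was given or received. Report completion separately for the three-injection regimen, and only when all three injections are documented, with dates from the chart review already planned. State a cut-off for this review that also covers Month 6 diagnoses; it cannot be shorter than 14 days from the first injection and should allow for late attendance. Make no completion claim for oral courses. Requiring three injections while counting a merely collected oral course as completed would apply two standards under one label.

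**Follow-up study visits.** Reword to say that treatment is given or started in clinic with stocked single-dose drugs, or prescribed for delivery to SHE Clinic within 48 hours, in line with Management of new diagnoses.

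**Cost.** A few sentences, a little more chart review (some of it after the exit visit), and possibly a slightly lower completion figure. No new visit is needed.
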